Prior to study commencement, approval will be obtained from the Institutional Review Board (IRB). Following IRB approval, and after explaining the study to and receiving consent from the attending physicians and ward nursing staff, the researcher will conduct participant recruitment in the inpatient wards and outpatient clinics. Individuals who meet the inclusion criteria will be identified as potential participants. The researcher will explain the study's purpose and methodology to these individuals. After obtaining informed consent and a signed consent form, the researcher will administer the pre-test (T0) questionnaires. This packet includes the Demographic Data Sheet, the Tang Fatigue Rating Scale (TFRS), the G-8 screening tool, and the symptom diary. This self-administration process is expected to take approximately 10 minutes. If a participant is unable or unwilling to self-report (e.g., due to advanced age or fatigue), the researcher will conduct a structured interview to complete the questionnaires, which is estimated to take 30–40 minutes. Concurrently, all participants will be invited to join the study's official LINE group for communication. Following the collection of baseline questionnaires, a computer-generated randomization sequence will be implemented by personnel not directly involved in the study (i.e., someone other than the principal investigator) to allocate participants to either the experimental group (Group A) or the control group (Group B). Participants in Group A, after confirming their chemotherapy infusion line is properly connected, will begin listening to 30 minutes of self-selected music while concurrently receiving standard care. Participants in Group B will receive standard care only. A total of **60 participants** with Acute Myeloid Leukemia (AML) undergoing chemotherapy are expected to be recruited (n=30 per group). Both groups will be required to complete the symptom diary throughout the 21-day

study period (est. 1 minute per entry). Group A will complete the Fatigue Numerical Rating Scale (NRS) immediately following each music therapy session. Group B will complete the Fatigue NRS 30 minutes after the commencement of their chemotherapy infusion.

On Day 21 (T1), the researcher will collect the post-test data (TFRS, NRS, and G-8) in the ward. If a participant has been discharged, data will be collected via telephone interview or an online questionnaire.

The laboratory data required for this study (WBC, Hb, Albumin) will be obtained by the researcher through a medical record review. Data from blood samples drawn as part of standard clinical care, taken before chemotherapy (T0) and on Day 21 (± 3 days) (T1), will be utilized. **No additional blood draws will be required for this study.**

Throughout the study period, participants may ask questions at any time via the official LINE group, and the researcher will provide responses.

Ethical Considerations

This study will be initiated only after obtaining approval from the Institutional Review Board (IRB) and securing consent from the nursing administrators and attending physicians of the recruitment site. Prior to formal enrollment, the researcher will personally explain the study's purpose, procedures, and methodology to each potential participant.

The researcher will address all participant inquiries. Participants will be explicitly informed that their participation is voluntary, that they may withdraw from the study at any time without penalty, and that their decision will not affect the quality of their medical treatment or nursing care in any way.

All research data collected from participants will be processed using anonymous coding. The data will be securely stored by the researcher and used exclusively for academic purposes. Confidentiality will be strictly maintained, and data will not be publicly disclosed or used for other purposes, ensuring the protection of participant privacy.

Data Processing and Statistical Analysis

1. Data Management The researcher will review all questionnaires for completeness. All collected data will be coded and entered into the Statistical Packages for the Social Sciences (SPSS) version 26.0 for data processing and management.

2. Statistical Analysis In accordance with the study's objectives, data analysis will be divided into descriptive and inferential statistics, as outlined in Table 3-3.

- **a. Descriptive Statistics:** Based on the characteristics of the variables, data

will be categorized into four measurement scales: nominal, ordinal, interval, and ratio (Kaur et al., 2018). Nominal and ordinal scale data are considered **categorical variables** (e.g., sex, education level, occupation, perceived economic status, marital status, religious beliefs, and chemotherapy drug names) and will be presented as frequencies (n) and percentages (%). Interval and ratio scale data are considered **continuous variables** (e.g., age, fatigue severity, Absolute Neutrophil Count [ANC], hemoglobin, and albumin) and will be presented using means, standard deviations (SD), and ranges (minimum and maximum) (Kaur et al., 2018).

- **b. Inferential Statistics:** This study utilizes an experimental design with longitudinal follow-up and repeated measures, analyzed on an **intention-to-treat (ITT)** basis. It will compare the differences in fatigue severity and clinical laboratory values between the music therapy and control groups. During the study, data attrition may occur due to factors such as disease progression or a participant's personal decision to withdraw, leading to unequal sample sizes at different measurement points. Therefore, this study will employ **Generalized Estimating Equations (GEE)** to analyze the relationship between the independent and dependent variables. GEE will be used to compare pre- and post-test values (fatigue severity, Absolute Neutrophil Count [ANC], hemoglobin, and albumin) between the experimental and control groups. A *p*-value of < 0.05 will be considered the standard for statistical significance (Ziegler & Vens, 2010).

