Moreno-Morales et al., 2020), psychiatric patients (Carr et al., 2013; Gassner et al., 2022; Gold et al., 2009; Köhler et al., 2020; Marquez-Garcia et al., 2021), and children with autism (Mayer-Benarous et al., 2021). Research by Sezgin et al. (2022) indicates that interventions—including the use of instruments, classical, modern, or personalized music therapy—typically last between 20–45 minutes, are conducted 1–2 times per week, and continue for 1–2 months (Burns et al., 2008; Sezgin & Bektas, 2022).

Although many studies have found that music therapy can reduce depression, anxiety, and pain in cancer patients, its application for managing fatigue is less common. This review identified six clinical trials that utilized music therapy as an intervention for fatigue in leukemia patients. The frequency, duration, intervention methods, and outcomes of these studies are summarized below (see Table 2-4).

All six studies involved leukemia patients aged 18 or older undergoing chemotherapy. Four of these clinical trials reported significant differences (Burns et al., 2008; Cassileth et al., 2003; Reimnitz et al., 2020; Miladinia et al., 2021), finding small to large effect sizes (ES, $d = 0.12$ – 1.95).

- **Burns et al. (2008)** randomized 49 patients into a music therapy (MT) group (N=25) and a standard care group (N=24). The MT group received 20-minute sessions twice weekly for one month (eight sessions total). Using The Functional Assessment of Chronic Illness Therapy - Fatigue (FACIT-F) scale, they found a significant difference in fatigue between the groups, showing a small effect (Cohen's $d = 0.12$, $p < 0.001$).
- **Cassileth et al. (2003)** randomized 62 patients undergoing autologous stem cell transplantation (ASCT) into an MT group (N=34) and a standard care group (N=28). The MT group received 20-minute sessions of individualized live music (vocal and instrumental, based on patient preference) for 3–7 weeks. Fatigue, measured by the POMS-Fatigue subscale, decreased significantly in the MT group (Cohen's $d = 0.21$, $p = 0.03$).
- **Reimnitz et al. (2020)** randomized 35 leukemia patients to an MT group (N=18) or a standard care group (N=17). The MT group received two 30-minute individual sessions of live music. The Visual Analogue Scale - Fatigue (VAS-F) showed a significant difference between groups, demonstrating a moderate effect (Cohen's $d = 0.78$, $p = 0.004$).

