9. Willing to cooperate with all study procedures during the research period.

Participants will be **excluded** from the study if they meet the following criteria:

1. Severe hearing impairment.

2. Unstable vital signs or unclear consciousness.

III: Sample Size Calculation

The sample size was estimated based on the **Generalized Estimating Equations (GEE)** approach for repeated measures. The analysis will control for baseline demographic and disease characteristics as covariates (e.g., age, sex, education level, occupation, perceived economic status, marital status, religious beliefs, and metastasis). The dependent variables are fatigue, White Blood Cell (WBC) count, hemoglobin, and albumin.

The calculation was performed using G*Power software (version 3.1.9.7). Parameters were set as follows: a significance level (α) of 0.05, statistical power ($1-\beta$) of 0.80, a 95% confidence interval, and an anticipated **effect size of 0.21**. This calculation yielded a required sample size of 34 participants (as shown in Figure 3-2). To account for a potential attrition rate of 30%, the study aims to recruit a total of **44 participants** ($n=22$ for Group A, $n=22$ for Group B).

Music Therapy Protocol

1. Music Selection, Dosage, and Headphone Use

According to the literature, a music therapy duration of 15–30 minutes is effective for fatigue alleviation (Burns et al., 2008; Cassileth et al., 2003; Miladinia et al., 2021; Reimnitz et al., 2020; Sezgin & Bektas, 2022). Music selection will be based on individual preferences and cultural background (Tsai & Chou, 2015; Browning, 2000; Gerdner, 2000).

To ensure data integrity while considering the patient's length of stay, physical burden during chemotherapy, and protocol adherence, the music therapy intervention in this study will be administered **once daily for 21 consecutive days**. The **30-minute intervention** will commence at the start of the chemotherapy infusion. During the study, participants will be provided with a chemotherapy symptom tracking diary to confirm adherence to the music therapy protocol in the experimental group.

For reasons of personal hygiene, preference, and potential patient discharge, participants will be asked to use their own headphones. If a participant does not have headphones, a set will be provided by the researcher.

Research Instruments and Psychometric Properties

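### The effect size of 0.21 behind 34 participants and 80% power has no stated source, metric or contrast, and its only match in the documents is a d that does not fit its own p-value

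*Combined protocol and SAP*

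**What the plan says.** Section III (Sample Size Calculation) names GEE for repeated measures and G*Power 3.1.9.7. It sets "a significance level (α) of 0.05, statistical power ($1-\beta$) of 0.80" and an anticipated "effect size of 0.21". It then reports: "This calculation yielded a required sample size of 34 participants". It does not say whether 0.21 is a d or an f, which study or contrast it comes from, how many measurements were entered, or what within-patient correlation was used. The software output is in a figure that is not shown in the text available here.

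Section II of the literature review (music therapy for cancer-related fatigue) contains one music-therapy effect of 0.21. That trial "randomized 62 patients undergoing autologous stem cell transplantation (ASCT) into an MT group (N=34) and a standard care group (N=28"), and its fatigue score "decreased significantly in the MT group (Cohen's $d = 0.21$, $p = 0.03"). Two neighbouring entries matter for the same check. The 49-patient trial (25 vs 24) is worded as a difference between groups, "showing a small effect (Cohen's $d = 0.12$, $p < 0.001"). The 35-patient trial (18 vs 17) is also worded as between groups, "demonstrating a moderate effect (Cohen's $d = 0.78$, $p = 0.004").

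Research Design and its Table 1 place the fatigue NRS at four time points, but the TFRS and the laboratory values at two (T0 and Day 21). The instruments section names the TFRS as the primary outcome measure.

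**The concern.** A between-arm standardised difference, the two group sizes and the p-value are tied together by arithmetic. For the transplant trial the three printed figures do not fit an ordinary two-arm test. If that trial supplied the planning value, the required 34 and the 80% power rest on an input whose meaning is unknown. It may be a correct between-arm d beside a p-value from some other analysis, a d extracted wrongly, or a within-arm change that says nothing direct about music against standard care.

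At stake is how a null result would be read. A reader told that power was 80% would take a null as evidence against a benefit, and that inference is sound only if the planning effect is.

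**Working it through.** **Inputs.** From the sample-size section: effect 0.21, α = 0.05, power 0.80, N = 34. From the literature review: d, p and arm sizes for the three trials. Assumed, because not stated: within-patient correlation ρ = 0.5, a two-sided α, and the repeated-measures within-between interaction test.

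**1. Reproducing 34.** For two groups and m measurements, λ = f²·N·m/(1 − ρ), df1 = m − 1, df2 = (N − 2)(m − 1). With f = 0.21, m = 4, ρ = 0.5, N = 34: λ = 0.0441 × 34 × 4 / 0.5 = 12.0 on 3 and 96 df, power 0.823. N = 32 gives 0.796, so 34 is the smallest even total. Other routes tried at 0.21 do not give 34:
- interaction with ρ = 0.5: 48 for m = 2 and 38 for m = 3;
- between-subject effect, m = 4, ρ = 0.5: 114;
- paired t-test: 180;
- two-sample t-test with d = 0.21: 356 to 357 per arm.

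This is a reconstruction, not proof. Other pairs of m and ρ come close (m = 3 with ρ = 0.6 gives 32).

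**2. The transplant trial.** t = d·√(n1·n2/(n1 + n2)) = 0.21 × √(34 × 28/62) = 0.21 × 3.92 = 0.82 on 60 df, two-sided p = 0.41 (0.40 to 0.42 over the rounding of d). A p of 0.03 needs t = 2.22, so d = 2.22/3.92 = 0.57.

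**3. What could reconcile d = 0.21 with p = 0.03.**
- Covariate adjustment: R² = 1 − (0.823/2.223)² = 0.86, a correlation of about 0.93.
- Comparison of change scores: correlation of about 0.93 (p = 0.032).
- Pre-post change within the 34 music patients, on the raw SD: t = 0.21·√34/√(2(1 − r)). At r = 0.5, t = 1.22, p = 0.23. At r = 0.85, t = 2.24, p = 0.032.

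**4. The neighbouring trials.**
- 25 vs 24, d = 0.12: t = 0.12 × 3.50 = 0.42, p = 0.68, against a printed p < 0.001. Reaching 0.001 needs d = 1.00, or covariates with R² of about 0.986.
- 18 vs 17, d = 0.78: t = 0.78 × 2.96 = 2.31, p = 0.028, against 0.004. Adjustment with R² = 1 − (2.306/3.094)² = 0.44 (correlation 0.67) closes the gap.

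**5. What each reading does to power.** Same interaction model, ρ = 0.5, f = d/2:

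| Between-arm d | f | m | Total N for 80% | Power at 34 |
|---|---|---|---|---|
| 0.21 | 0.105 | 4 | 126 | 26% |
| 0.21 | 0.105 | 2 | 180 | 22% |
| 0.42 (entered f = 0.21) | 0.21 | 4 | 34 | 82% |
| 0.42 (entered f = 0.21) | 0.21 | 2 | 48 | 66% |
| 0.57 | 0.2835 | 4 | 20 | 98% |
| 0.57 | 0.2835 | 2 | 28 | 89% |

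With m = 4 and ρ from 0.3 to 0.7, power at 34 runs from 20% to 42% at d = 0.21, and from 92% to nearly 100% at d = 0.57.

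**The case against.** The strongest reply has four parts.

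- **The transplant entry is ambiguous, not contradictory.** It describes a decrease in the music arm and names no test or adjustment. A within-arm test with r about 0.85 makes d and p agree. This stands. It does not rescue 0.21 as a planning value, because a within-arm change does not measure music against standard care. The 49-patient entry has no such escape: it is worded as between groups and would need covariates explaining almost all the variance.
- **The link to the sample size is a match of two numbers.** This also stands. If the link is wrong, 0.21 has no documented basis at all, and the request to name its source is unchanged.
- **The 35-patient mismatch is weak evidence.** Agreed: its d is significant on a plain test, and ordinary baseline adjustment could account for the rest.
- **A mismatch does not show that 0.21 is too large.** Agreed. If p = 0.03 is a correct unadjusted between-arm result, d is about 0.57, and 34 patients exceed 80% power in the model that reproduces 34.

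A reader might therefore infer that 80% power fails under every reading, or that the trial is shown to be underpowered. The documents do not support either. Lower figures can be had at d = 0.57: a Day 21 comparison adjusted for T0, with assumed r = 0.5 and 17 per arm, gives 46%. That comes from changing the analysis model, not from the disagreement between d and p.

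**Conclusion.** The point holds as a lack of support, not as proof of a wrong sample size. The 34 and the 80% rest on an unsourced 0.21. Its only match in the documents is a d that fits its p-value only under a very high correlation. Read as a between-arm d in the model that reproduces 34, it gives about 26% power instead of 80%; if the p-value is the sound figure, power is about 98%. Which applies cannot be settled without the cited trial.

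The size rests on three assumptions: the inferred source, the reconstructed software settings (m = 4, ρ = 0.5), and f = d/2. The last favours the plan. If the arms are equal at T0 and differ by d only at Day 21, the two-measurement interaction effects are ±d/4, so f = d/4. With ρ = 0.5, power at 34 is then 9% at d = 0.21 and 36% at d = 0.57. The upper rows of the table are therefore no reassurance until the assumed pattern over time is stated. Separately, four measurements fit the NRS but not the TFRS; with two, even f = 0.21 gives 66% at 34.

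**What to change.** In Section III (Sample Size Calculation):

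1. Name the trial, contrast (between-arm or within-arm) and metric (d or f) of 0.21.
2. Check it against that trial's between-arm means, SDs and group sizes. Replace it if it is a within-arm change or was extracted wrongly. Recheck the 49- and 35-patient entries in the same way.
3. Convert d to f for the pattern over time that is assumed. State the number of measurements (two for the TFRS, T0 and Day 21) and the correlation.
4. Restate the power of the planned number, after attrition, over a plausible range such as d = 0.21 to 0.57. Say which planned number applies, since Research Procedures gives 60 and the other sections 44.

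The cost is a few hours of re-extraction and a reworded paragraph, with no added patients or procedures. The downside is that the stated power may look less favourable.

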Based on the literature review, CRF is a significant and distressing problem for leukemia patients. Due to the disease itself, considerations for hemoglobin, platelets, and patient activity safety severely limit the available intervention options for fatigue. Music therapy is a non-invasive, safe, comfortable, and easily administered nursing intervention. Following appropriate assessment and selection of resonant music based on client preferences, it can be implemented by healthcare providers or by the patients' families.

Discrepancies exist between domestic (Taiwanese) and international music therapy practices, primarily in education systems, professional certification, legal regulations, and cultural factors. Currently, Taiwan lacks a formal certification system for music

therapists, unlike many other countries. Compounded by financial constraints that often preclude hiring therapists with foreign qualifications, the implementation of standardized MT is challenging.

Therefore, this study aims to recruit patients newly diagnosed with leukemia who are undergoing conventional chemotherapy. It will utilize music therapy as an intervention to investigate its effects on fatigue and clinical laboratory values.

Research Methods

This chapter is divided into nine sections, detailing the methods and procedures of this study. It includes: (1) research framework, (2) research design, (3) research setting and participants, (4) sample size, (5) the music therapy protocol, (6) research instruments and reliability/validity, (7) research procedures, (8) ethical considerations, and (9) data processing and analysis.

Research Framework

Based on the aforementioned literature review, the research framework for this study was developed as illustrated in Figure 3-1.

The primary purpose of this study is to investigate the effects of music therapy on fatigue and clinical laboratory values (e.g., White Blood Cell [WBC] count, Hemoglobin [Hb], Albumin) in patients with acute leukemia undergoing chemotherapy. The study is designed to provide music therapy to this patient population, utilizing fatigue severity and clinical laboratory values as the primary outcome variables. This framework will be used to compare the differences in these key outcome variables between the music therapy group and the standard care group.

Research Design

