1. Participant Demographic Data Sheet Data will be collected using Google Forms or paper questionnaires, as appropriate. This sheet includes demographic information such as age, sex, education level, occupation, perceived economic status, marital status, and religious beliefs, to be completed by the participant. The questionnaire also

includes items regarding the participant's prior musical training, frequency of daily music listening, motivations for listening, typical timing and methods of listening, and preferred activities during rest.

2. Leukemia-Related Treatment Data Sheet This data will be extracted from the patient's medical records by the researcher. It includes information on chemotherapy drugs and dosages, as well as laboratory values—specifically Absolute Neutrophil Count (ANC), Hemoglobin (Hb), and Albumin—from before chemotherapy (T0) and on Day 21 (T1).

3. Tang Fatigue Rating Scale (TFRS) While many reliable and valid fatigue scales exist globally, many have limitations. Considering that fatigue assessment should encompass physical, psychological, and activity dimensions, the TFRS was selected as the primary outcome measure for this study.

The TFRS contains 37 items across three subscales: Physical (15 items), Psychosocial (12 items), and Daily-Living (10 items). It uses a 10-point rating scale, where higher scores indicate greater fatigue severity. The TFRS underwent content validity testing by three PhD-level experts in fatigue theory and psychometrics. It was validated in a sample of 107 patients with chronic heart failure. The internal consistency (Cronbach's α) was 0.96 for the total scale, and 0.83 (Physical), 0.92 (Psychosocial), and 0.97 (Daily-Living) for the subscales. The TFRS demonstrated excellent validity: **convergent validity** with the Visual Analogue Scale for Fatigue (VAS-F) was 0.87, and **construct validity** with The Beck Depression Inventory-Second Edition (BDI-II) was 0.77 (Tang et al., 2010).

In the study by Tang et al. (2010), the TFRS also showed a significant positive correlation with the New York Heart Association (NYHA) functional class ($r = 0.75, p < 0.01$) and significant negative correlations with Ejection Fraction (EF) ($r = -0.46, p < 0.01$) and Hemoglobin (Hb) ($r = -0.27, p < 0.01$) (Tang et al., 2010).

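### The plan gives conflicting accounts of what is primary, sets no success rule for four outcomes tested at 0.05, and switches the white-cell outcome from WBC to ANC

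*Combined protocol and SAP*

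**What the plan says.** **What is primary.** The Research Framework names WBC, hemoglobin and albumin as the laboratory values and describes the study as "utilizing fatigue severity and clinical laboratory values as the primary outcome variables". Under Research Instruments and Psychometric Properties, item 3 says "the TFRS was selected as the primary outcome measure for this study". Research Design gives a single objective, which is to relieve fatigue. Section 2 (Research Hypotheses) has two directional hypotheses, one on fatigue and one on the three laboratory values joined by *and*.

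**What is tested, and at what level.** The sample size section uses one alpha of 0.05 and says "The dependent variables are fatigue, White Blood Cell (WBC) count, hemoglobin, and albumin". Under Data Processing and Statistical Analysis, item 2b, the inferential plan is stated as "It will compare the differences in fatigue severity and clinical laboratory values between the music therapy and control groups". GEE is then applied to "pre- and post-test values (fatigue severity, Absolute Neutrophil Count [ANC], hemoglobin, and albumin) between the experimental and control groups", and a "value of < 0.05 will be considered the standard for statistical significance". No adjustment, order of testing or rule for trial success follows. The section points to Table 3-3, which is not in the readable text.

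**Which white-cell count.** Research Procedures says "The laboratory data required for this study (WBC, Hb, Albumin) will be obtained by the researcher". The treatment data sheet (instruments, item 2) lists laboratory values as "specifically Absolute Neutrophil Count (ANC), Hemoglobin (Hb), and Albumin", and the GEE comparison also uses ANC.

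**The concern.** A reader of the final report needs to know which result decides whether the trial succeeded. Here the Research Framework can be read as four co-primary outcomes, and the instruments section as one. Nothing visible says whether one significant result is enough, whether all are needed, or which comes first. The choice could therefore be made after the data are seen. On the widest reading, a lone p < 0.05 on albumin or hemoglobin could be reported as a positive primary result although fatigue, the stated objective, shows no difference.

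The white-cell mismatch widens that freedom. WBC and ANC are different counts, and the analysis section does not name the one in hypothesis 2.

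**Working it through.** **1. The plan's own figure.** The plan states no overall error rate. Its nearest figure is the required sample of 34, at alpha 0.05, power 0.80 and effect size 0.21. Three inputs are not stated, so I assumed that 0.21 is Cohen's f, that there are four measurements, and that the correlation between measurements is 0.5. For a group-by-time interaction with two groups, the noncentrality is f²·N·m/(1 − r) = 0.21² × 34 × 4 / 0.5 = 12.0. On 3 and 96 degrees of freedom the power is 0.82, so 34 is reproduced. The alpha in it is an unadjusted 0.05 for one test. Four measurements fit only the numerical rating scale (NRS); Table 1 schedules the TFRS and the laboratory values twice.

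**2. Any one of four may count (Research Framework reading).** Assume no true effect and two-sided tests, since sidedness is not stated.

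- Independent outcomes, two-sided: 1 − 0.95⁴ = 0.185.
- Independent outcomes, favourable direction only: 1 − 0.975⁴ = 0.096, against 0.025 for one outcome.
- Correlated outcomes: four normal test statistics with common correlation r, by numerical integration.

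| Common r | Any of four at 0.05, two-sided | Favourable direction only | Four tests at 0.0125, two-sided |
|---|---|---|---|
| 0 | 18.5% | 9.6% | 4.9% |
| 0.5 | 15.6% | 7.8% | 4.3% |
| 0.8 | 11.4% | 5.7% | 3.2% |
| 0.9 | 9.4% | 4.7% | 2.6% |

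The two-sided rate tends to 5% as r approaches 1, so no row is a floor.

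**3. False laboratory result while fatigue is not significant.** This is the any-of-four rate less the 5% in which fatigue itself is falsely significant: 18.5 − 5 = 13.5% if independent, 15.6 − 5 = 10.6% at r = 0.5, and 11.4 − 5 = 6.4% at r = 0.8.

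**4. Readings with no material inflation.**

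- TFRS alone is primary: 5%.
- Fatigue, or all three laboratory values together: if independent, 1 − 0.95 × (1 − 0.05³) = 0.0501. By simulation it is 5.2% at r = 0.5 and 5.4% at r = 0.8.

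**5. How many fatigue tests.** The analysis section does not say whether fatigue severity means the TFRS, the NRS or both. If both are tested there are five tests: 1 − 0.95⁵ = 22.6% if independent, and 12.7% at r = 0.8.

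**6. White-cell outcome, side by side.**

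| Place | Variable |
|---|---|
| Section 2, hypothesis 2 | WBC |
| Research Framework | WBC |
| Table 1 | WBC |
| Sample size section | WBC |
| Research Procedures | WBC |
| Treatment data sheet | ANC |
| Descriptive statistics and GEE comparison | ANC |

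This conflict needs no assumption: the variable in hypothesis 2 is not the one named for testing.

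**The case against.** The strongest reply is that the plan does contain a hierarchy: the instruments section names the TFRS as primary and Research Design makes fatigue the objective. The Research Framework might be using *primary* loosely for its main dependent variables; its next sentence calls them key outcomes. This has weight, and it would be wrong to say that the plan gives no indication of priority. But the TFRS sentence sits in a paragraph on choosing among fatigue scales and may only name the fatigue instrument. If it names the sole primary outcome, it contradicts the Research Framework. Either way the sections need reconciling.

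Second, no passage says that one significant result makes the trial positive, and hypothesis 2 joins its three laboratory values with *and*. That stands. A reader might infer that the plan commits the trial to a false-positive rate of 11% to 19%. The documents do not support this: those figures hold only if any one outcome may count, and only for correlations from 0 to about 0.8. Equally, no passage says that all three laboratory values must be significant.

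Third, Table 3-3 is said to outline the analysis and is not shown. It could hold a rule, so the absence is established only for the readable text. The body text would still conflict on what is primary and on WBC against ANC.

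Fourth, the hypotheses are directional. Counting only false favourable results, the any-of-four rate is 9.6% to 5.7% for correlations from 0 to 0.8, against 2.5% for one outcome. That is lower in absolute terms but still a multiple of the single-outcome rate.

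**Conclusion.** The concern holds as an unresolved conflict over the primary outcome, together with a mismatch in the white-cell variable. It is not proof of an inflated error rate. Depending on the reading, the two-sided false-positive chance runs from 5% (TFRS alone), or about 5% (fatigue, or all three laboratory values), to 18.5% (any one of four, independent). The last falls to 15.6%, 11.4% and 9.4% at common correlations of 0.5, 0.8 and 0.9. These figures rest on two-sided tests, a common correlation, fatigue counted once and no true effect.

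The WBC/ANC conflict is plain from the text. A reader might infer from it that WBC is not collected; Table 1 and Research Procedures show that it is.

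The matter should be fixed but is not fatal. Confidence is medium, because the analysis table and the framework figure cannot be seen.

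**What to change.** Before any group comparison, amend the Research Framework and the inferential statistics paragraph to state one rule.

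- **Preferred.** The between-group difference in TFRS total score at Day 21, estimated from the planned GEE, is the single primary outcome at two-sided 0.05. This agrees with Research Design and the instruments section. The NRS, WBC, hemoglobin and albumin are secondary. They are tested by Holm (smallest p against 0.0125, then 0.0167, 0.025 and 0.05) only if the TFRS is significant; otherwise they are reported as supportive.
- **If four primaries are kept.** Use Holm, or Bonferroni at 0.05/4 = 0.0125 each. Either holds the overall error at or below 5%.

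Under both options, name the fatigue instrument and use one white-cell variable throughout. WBC matches hypothesis 2 and Table 1; the treatment data sheet, descriptive statistics and GEE comparison would then change from ANC.

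The cost is a text amendment. Laboratory claims face a stricter standard under both options, and hypothesis 2 becomes secondary under the first. The power statement must be restated for the chosen outcome and test, giving the type of the 0.21 effect size, the number of measurements and the assumed correlation. I give no replacement power figure because it depends on those choices.
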